^b Value calculated for a 60-kg human.

- ^c Value from ICH S9 Guideline: "Nonclinical Evaluation for Anticancer Pharmaceuticals" (ICH, 2009).
- ^d Using the allometry-derived plasma clearance (18.9 L/hr) and volume of distribution (1.44 L/kg) estimates, the predicted steady state C_{5 min} and systemic exposure (AUC_{24hr}) of CC-90009 following daily administration of a 0.3 mg IV infusion dose in a 60-kg human are 3.4 ng/mL and 15.7 ng·hr/mL, respectively.
- ^e Predicted exposure multiple equals animal value divided by predicted human value at each corresponding human starting dose.

Refer to the Investigator's Brochure for detailed information.

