
1.3.5 Rationale for Pharmacodynamics and Potential Predictive Biomarkers

The therapeutic hypothesis for CC-90009 activity in AML and MDS is that CBRN-dependent substrate degradation and induction of UPR preferentially kill leukemic cells, and a therapeutic index of 2- to 5-fold over normal hematopoietic stem cells can be achieved with intermittent dosing. CC-90009 binding to the CRL4^{CRBN} complex promotes ubiquitination and degradation of

substrates. Substrate degradation by CC-90009 leads to activation of the UPR pathway and induces apoptosis in AML cells.

CC-90009 is broadly active at killing leukemic cells in ex-vivo cultures of primary bone marrow cells from AML patients, while a spectrum of sensitivities have been observed across a 20 cell line AML panel. In vitro studies in AML cell lines show that the extent of CRBN-dependent substrate reduction by CC-90009 is predictive of apoptosis sensitivity.

Blood will be collected predose and postdose for the purpose of measuring PD markers of CC-90009 activity. Priority PD endpoints include quantification of CBRN substrates and quantification of markers of UPR and nonsense-mediated decay (NMD). A portion of bone marrow tissue (biopsy and aspirate), collected before and during treatment, will also be utilized for evaluation of PD endpoints.

Ongoing studies are evaluating the exposure-response relationships to PD and efficacy endpoints to model the dose and exposure profile predicted to affect biologic and clinical activity with CC-90009 therapy. This modeling along with PD data collected will be used to support decisions about dose and schedule during the study. In the expansion phase of the study, the relationship between PD markers and safety and/or efficacy will be further explored in both AML and HR-MDS cohorts.

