6.6.2 Pharmacodynamic Biomarker Blood Samples

The schedules for blood collections for pharmacodynamic biomarkers are provided in Table 9 and Table 10.

Table 9:Sample Collection of Blood for Pharmacodynamic Biomarkers on D1-5Schedule and Alternative Schedules with up to 10 consecutive dosing
days (eg, D1-7 and D1-10) for Part A or Part B

			Cycle 1 ^a									
	Screeni ng	D	ay 1	Day	Day 2		Day 3		Last Day of Dosing	Day 8 ^b	Day 15	Day 28 ^d
Sample	Day - 14 to -1°	Pred ose (≤ 3 hrs)	6 hours (± 15 min) after EOI	Predose (≤ 3 hrs)	6 hours (± 15 min) after EOI	Predose (≤ 3 hrs)	6 hours (± 15 min) after EOI	Predose (≤ 3 hrs)	6 hours (± 2 hr) after EOI	AM	AM	AM
Whole blood, flow cytometry ^a	Х	Х	Х	X ^g	Xg	X	Х			Х	Xg	Х
Whole blood, PD biomarkers	X ^d								X ^{d,e}			X ^{d,e}
Blood for PBMC, PD protein & RNA ^a	Х	Х		X ^g		Х				Х		
Blood for PBMCs, ex vivo sensitivity assays, phenotyping & sequencing		Х										
Blood for plasma, cytokine assays	X	Х		Х		Х		Х		Х		
SARS-CoV-2 Serology ^f		Х										

Abbreviations: AM = morning; EOI = end of infusion/injection; PBMC = peripheral blood mononuclear cells; PD = pharmacodynamic; RNA = ribonucleic acid; SARS-CoV-2 = severe acute respiratory syndrome coronavirus 2.

- ^a If intra-subject dose escalation occurs, blood samples for PD assays will also be collected during the first cycle at the increased dose on Days 1, 2, 3, 4, 8 and 15; see laboratory manual for details.
- ^b If Day 8 is a dosing day due to use of an alternate schedule per the SRC, obtain samples pre-dose.
- ^c Obtaining the Screening samples on the same day as the Screening bone marrow aspirate and biopsy is preferred.
- ^d For subjects in Part B only. Last day of dosing is defined as the last consecutive planned day (eg, Day 5 on the Days 1-5 schedule or Day 7 of the Days 1-7 schedule). See also footnote e and Section 6.6.3 for allowable days for the Cycle 1 Last Day of Dosing sample collection (ie, on Days 1-5 schedule, Day 4 or 5; on Days 1-7 schedule, Day 6, 7, or 8).

^e Collected the same day the bone marrow samples are collected for PD or response assessments in Cycles 1, 2 and 4

^f Serum collected to be used for possible measurements of anti-SARS-CoV-2 serology (anti-SARS-CoV-2 total or IgG (see Table 6)

^g For Part A only.

		Cycle 1											
	Screening	D	ay 1	Day 2	Day 3	Day 4	Day 8	Day 9	Day 15	Day 22			

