6.6.3 Pharmacodynamic Biomarker Bone Marrow Samples

Bone marrow aspirates and biopsy for PD and prognostic/predictive biomarkers will be collected at the time points indicated in Table 4 – Table 7, Appendix K, or Appendices M-O. Exploratory tests may be performed to determine Minimal Residual Disease (MRD) status at efficacy time points. In Cycle 1 on Day 5 on the D1-5 dosing schedule, the PD samples will be collected between 4 to 8 hours after CC-90009 is administered. If necessary due to scheduling conflicts, the PD samples may be collected on Day 4 (4 to 8 hours after dosing). If the dosing interval (schedule) is extended, then samples will be obtained on the last day \pm 1 day (ie, if extended to consecutive 7 days or 10 days, the PD bone marrow sample can be collected on Day 6-8 [Appendix M] or 9-11 [Appendix O]). For the D1-3/D8-10 schedule, the PD bone marrow sample is collected on Day 9 or 10 (Appendix K).

Additionally, bone marrow aspirates and/or biopsies may be obtained in both Part A and Part B, after a CR is confirmed, if relapse is suspected, or following treatment discontinuation to elucidate effects of long-term treatment or resistance mechanisms, or as clinically indicated based on the Investigator's medical assessment. When obtained for any of the reasons above, samples for biomarker assessments will also be collected at the same time.

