Appendix N: Part B Table of Events for D1-7 Dosing Schedule

Table 35:Table of Events for Part B (D1-7 Schedule) of Cycle 1

						Ті	reatment Pe	riod				
	Screening						Cycle 1					
					WK1				WK2	WK3	W	'K4
Events ^a	D-28 to -1	D1	D2	D3	D4	D5	D6	D7	D8	D15	D22	D28 ^c
Study Entry (Section 6.1)												
Informed consent	Х											
Inclusion/ exclusion criteria	Х											
Medical ^{t/} oncologic history	Х											
AML or MDS Disease Assessment and Cohort Assignment ^b	Х											
Demographics	Х											
IRT registration	Х	Х										
Pregnancy risk counseling and contraceptive compliance confirmation	Х				As specifi	ed in Sectio	on 6.1.1 and	the PPP in	Appendix L	_		
Prior/ concomitant medications & procedures (Section 6.2.1)	Х	Х	Х	Х	Х	Х	Х	Х	Х	Х	Х	
CC-90009 Administration (Section	n 7)											
Calcium, calcitriol, and vitamin D supplements and recording on diary card (refer to Section 7.2)	X (D-3 to D-1)	Х	x	х	X	х	х	х	X ^d			
Provide/review diary card	Х	Х										
Corticosteroid administration (dexamethasone) (refer to Section 7.2) for doses 3.6 mg and above		Х	Х	Х	х	Х	х	Х				
IV administration of CC-90009		Х	Х	Х	X	X	Х	Х				

Table 35:Table of Events for Part B (D1-7 Schedule) of Cycle 1

						Ті	eatment Pe	riod				
	Screening						Cycle 1					
					WK1				WK2	WK3	W	K4
Events ^a	D-28 to -1	D1	D2	D3	D4	D5	D6	D7	D8	D15	D22	D28c
Monitoring as an inpatient		Х	Х	Х	X	Х	Х	Х				
Safety Assessments (Section 6)												
Adverse Event Evaluation (Section 6.2.2)	X	Х	Х	Х	Х	Х	Х	X	X	Х	Х	
Height	X											
Weight (Section 6.2.3)	X	Х							Х	Х	Х	
Vital Signs (Section 6.2.3)	Х	Xf	Xf	Xf	Xf	Xf	Xf	Xf	Х	Х	Х	
Physical Examination (Section 6.2.4)	X	Х							X			
ECOG PS (Appendix D)	Х	Х							Х			
SARS-CoV-2 Viral Testing ^r	X (within 7 days of D1)											
12-lead ECG (in triplicate, Section 6.2.5)	X (≥72 hrs prior to D1)	Xf						Xf	X			
Adverse Event Evaluation (Section 6.2.2)	Х	Х	Х	х	х	Х	Х	Х	X	Х	Х	
Height	Х											
Weight (Section 6.2.3)	Х	Х							Х	Х	Х	
Vital Signs (Section 6.2.3)	Х	Xf	Xf	Xf	Xf	Xf	Xf	Xf	Х	Х	Х	
Physical Examination (Section 6.2.4)	X	Х							X			
Safety Assessments (Section 6)				•								·
ECOG PS (Appendix D)	Х	Х							Х			

Table 35:Table of Events for Part B (D1-7 Schedule) of Cycle 1

						Tr	reatment Pe	riod				
	Screening						Cycle 1					
					WK1				WK2	WK3	W	/K4
Events ^a	D-28 to -1	D1	D2	D3	D4	D5	D6	D7	D8	D15	D22	D28 ^c

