- ⁿ Obtained between 4 to 8 hours postdose. The samples may be obtained on Day 6 or on Day 8 if necessary due to scheduling difficulties. If the dosing interval (schedule) is extended, then samples will be obtained on the last day ±1 day of dosing (eg, if extended to 10 day, obtain on Day 9-11).
- ^o Additional aspirates and biopsies will be collected as clinically indicated (eg, Cycle 1 Day 15 based on Investigator's medical assessment).
- ^p Molecular and cytogenetic studies may be omitted at: Screening, if they were completed within the previous 90 days and the results are available for recording on the electronic case report forms; see Section 6.1 for details on sending samples to the central laboratory.
- ^q Urine PK to be performed on approximately 10 selected subjects from Part A and/or Part B. This is a 24-hour collection that starts C1D1 and ends C1D2.
- ^r RT-PCR testing for SARS-CoV-2 is mandatory within 7 days prior to first dose of CC-90009 (C1D1). The RT-PCR test should be based on institutional or local guidelines. Please see Section 6.1 in the event of a positive result.
- ^s Serum will be collected at predose on Cycle 1 Day 1 (or at screening), approximately every 6 months during study treatment and at EOT to be used for possible measurements of anti-SARS-CoV-2 serology (anti-SARS-CoV-2 total or IgG). Results will not be used to determine eligibility. Serum should also be collected approximately 4 weeks after a documented or suspected SARS-CoV-2 infection.
- ^t Medical history will also include COVID-19 vaccines, toxicities of prior treatments, and known allergies.

Table 36:Table of Events for Part B (D1-7 Schedule) of Cycles ≥ 2

	Treatment Period													Period
Events ^a														
	WK1								WK2 WK3		WK4	EOT ^b	Safety ^c	
	D1	D2	D3	D4	D5	D6	D7	D8	D15	D22	D28	≤28 days	28 days (± 3 days)	Long Term
Review concomitant medications & procedures (Section 6.2.1)	Х	Х	Х	Х	Х	Х	Х	Х	Х	Х	Х	Х	Х	
				CC	-90009 A	dminist	ration (S	Section 7)		•				
Calcium, calcitriol and Vitamin D supplements and recording on diary card (Section 7.2)	Х	Х	Х	Х	Х	х	Х	X ^d			$X (C2 and C3)^d$			
Provide/ review of diary card	Х											Х		
Corticosteroid administration (dexamethasone) (refer to Section 7.2) for doses 3.6 mg and above	Х	Х	Х	Х	Х	x	Х							
IV administration of CC-90009 ^e	Х	Х	Х	Х	Х	Х	Х							
					Safety A	ssessme	nts (Sect	ion 6)						
Adverse Event Evaluation (Section 6.2.2)	Х	Х	Х	Х	Х	Х	Х	Х	Х	Х		X	Х	
Weight (Section 6.2.3)	Х											Х		

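### Part B Days 1-7: the Cycle 1 PD marrow and paired blood are due 4 to 8 hours postdose, yet Day 8, with no planned dose, is also allowed under the same nominal time point

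*Combined protocol and SAP*

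**What the plan says.** Table 35 footnote n in Appendix N is attached to the Day 7 entries for the PD bone marrow and for the whole-blood PD biomarker: "Obtained between 4 to 8 hours postdose. The samples may be obtained on Day 6 or on Day 8 if necessary due to scheduling difficulties". In the same table the row "IV administration of CC-90009" is marked on Days 1 to 7 and is blank on Day 8.

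Table 9 (Section 6.6.2) puts the paired whole-blood sample in a last-day-of-dosing column timed at 6 hours (± 2 hours) after the end of infusion. Footnote d defines that day as Day 7 on this schedule, yet accepts "on Days 1-7 schedule, Day 6, 7, or 8".

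Section 6.6.3 gives an hour window for Days 1-5: "the PD samples will be collected between 4 to 8 hours after CC-90009 is administered". Its fallback is also a dosing day: "If necessary due to scheduling conflicts, the PD samples may be collected on Day 4 (4 to 8 hours after dosing". For longer schedules it says "if extended to consecutive 7 days or 10 days, the PD bone marrow sample can be collected on Day 6-8", and gives no hours.

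Section 9.9.2 compares biomarker levels before and during treatment with a Wilcoxon signed rank test. It has no rule for samples outside their window. On the use of PD results, Section 1.3.5 says: "This modeling along with PD data collected will be used to support decisions about dose and schedule during the study".

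**The concern.** A site that follows footnote n as written cannot normally satisfy both of its sentences on Day 8. It can choose Day 8, comply with the listed days and miss the listed hours. The sample would still be filed under the last day of dosing. Samples from about 6 hours and from about 24 hours or more after a dose would then carry one nominal label.

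The 2.4 mg and 3.0 mg Days 1-7 cohorts are the ones opened for dose optimization and sepsis mitigation (Section 1.2.3.1), and PD data feed dose and schedule decisions. Each safety run-in has up to 6 subjects, so one or two off-window samples would be 1/6 (17%) or 2/6 (33%) of a run-in summary. Table 9 also has its own Day 8 morning column for other PD samples, so the plan elsewhere treats Day 8 as a separate time point.

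**Working it through.** **1. The sampling rules side by side**

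| Schedule and source | Last planned dose | Days allowed | Hour window | Are all allowed days dosing days? |
|---|---|---|---|---|
| Days 1-5 (6.6.3; Table 6 footnote n) | Day 5 | 5 or 4 | 4 to 8 h | Yes |
| Days 1-3/8-10 (6.6.3; Table 31 footnote n) | Day 10 | 10 or 9 | 4 to 8 h | Yes |
| Days 1-7 marrow and blood (Table 35 footnote n) | Day 7 | 7, 6 or 8 | 4 to 8 h | No |
| Days 1-7 paired blood (Table 9) | Day 7 | 6, 7 or 8 | 6 ± 2 h after end of infusion | No |
| Days 1-7 marrow (6.6.3) | Day 7 | 6 to 8 | none given | No |

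Table 33 (Part A, Days 1-7) repeats the text of footnote n. Table 37 (Part A, Days 1-10) carries the Day 6 or Day 8 wording although its marrow is marked on Day 10.

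**2. Can a Day 8 sample fall in the window?** The window closes 8 hours after the dose. It reaches past midnight only if the Day 7 dose is given after 24:00 − 8 h = 16:00. With an 08:00 dose on Day 7, the window is 12:00 to 16:00 that day, and a sample at 08:00 to 16:00 on Day 8 is 24 to 32 hours postdose. The other route is an interruption that makes Day 8 a dosing day, since Section 7.2.12 lets Cycle 1 doses run to Day 10.

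**3. How different is the drug level?** Table 1 footnote d (Section 1.3.3) gives the predicted PK: "Using the allometry-derived plasma clearance (18.9 L/hr) and volume of distribution (1.44 L/kg) estimates", for a 60 kg human. So V = 1.44 × 60 = 86.4 L, k = CL/V = 18.9/86.4 = 0.219 per hour, and half-life = 0.693/0.219 = 3.2 h.

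A one-compartment model reproduces the plan's own figures for 0.3 mg (300 µg):

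- AUC = dose/CL = 300/18.9 = 15.9 ng·h/mL (stated 15.7).
- C5min = (dose/V) × exp(−k × 5/60) = (300/86.4) × exp(−0.018) = 3.4 ng/mL (stated 3.4).

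The Day 8 level relative to the in-window level is exp(−k × gap). Two contrasts cover the range: 28 h against 6 h (gap 22 h, mid-points) and 24 h against 8 h (gap 16 h, the smallest). Section 1.2.3.1 also reports observed median AUC24 values of 106 ng·h/mL without strong CYP3A4 inhibitors and 192 with them. The second is called dose-normalized, but no reference dose is stated. I assume both are per 1 mg, so CL = 1000/AUC24, and keep V = 86.4 L.

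| PK basis | CL (L/h) | k (per h) | Half-life (h) | 28 h vs 6 h | 24 h vs 8 h |
|---|---|---|---|---|---|
| Predicted | 18.9 | 0.219 | 3.2 | 0.8% | 3.0% |
| AUC24 106 per 1 mg | 9.4 | 0.109 | 6.4 | 9.1% | 17.4% |
| AUC24 192 per 1 mg (strong inhibitor) | 5.2 | 0.060 | 11.5 | 27% | 38% |

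If the 106 were per 3 mg instead (CL 28.3 L/h, k = 0.328), both ratios would be below 1% (0.07% and 0.5%).

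**4. What this does not give.** These are plasma drug ratios. The documents contain no marrow PD time course after the last dose, so they cannot be converted into a change in the PD marker.

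**The case against.** The strongest reply is that Day 8 is deliberate flexibility. It appears in Section 6.6.3, Table 9 and two tables of events, and 6.6.3 ties the 4 to 8 hour window to Days 1-5 only. Footnote n's second sentence might then be read as an exception to its first. That has some force, but the exception leaves Day 8 with no stated time, and Table 9 still requires 6 ± 2 hours after infusion for the paired blood.

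Day 8 also has a practical use. With a Monday start, Days 6 and 7 are a weekend, and a ban could lose mandatory marrows. This stands, and it is why the fix does not require one.

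The stakes are limited. PD endpoints are exploratory (Table 3), such data may be left out of the study report (Table 2), and no power calculation or stopping rule depends on this sample. Table 8 schedules a PK sample 24 hours after the last Cycle 1 dose, so a nearly concurrent drug level should exist for a Day 8 marrow.

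Three stronger readings are tempting, and the documents do not support them:

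- *Day 8 samples are washed out.* Nothing says so. Section 1.3.4 reports GSPT1 degradation maintained through the dosing period at 3.6 mg, which spans intervals of about 24 hours. That evidence is in peripheral blood at another dose, so it does not settle the matter for marrow at 2.4 or 3.0 mg either.
- *The analysis pools the two kinds of sample.* Section 9.9.2 neither pools nor separates them. Laboratory Manual instructions on PD samples were not available for this review.
- *The comparison of 2.4 mg with 3.0 mg is confounded.* Nothing suggests that Day 8 would be used more often in one cohort, and no formal PD comparison of the two is planned.

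**Conclusion.** The conflict is real. On an uninterrupted Days 1-7 schedule with the Day 7 dose given by 16:00, the Day 8 option cannot meet the 4 to 8 hour window in footnote n or the 6 ± 2 hour column in Table 9. Such a sample is nearer a trough than an in-window reading, with plasma drug at roughly 1% to 38% of the in-window level. That range assumes one compartment, the predicted volume, dosing and sampling times that put Day 8 at 24 to 32 hours, and either predicted clearance or AUC24 per 1 mg. The lower end falls further if the AUC24 reference dose is larger.

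The size and direction of any effect on the PD marker are unknown. What is established is a labelling fault in an exploratory readout that informs dose selection, and the absence of a rule for handling it. Claims of washout, of actual pooling or of confounding between dose cohorts go beyond the documents.

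**What to change.** 1. Reconcile Table 35 footnote n, Section 6.6.3 and Table 9 footnote d so that they give the same days and hours for Days 1-7. Prefer a dosing-day fallback (Day 6, at 4 to 8 hours postdose), in line with Day 4 on Days 1-5.
2. Bring the matching text in Tables 33 and 37 into line. Part A enrollment is complete, so for those samples the gain is correct labelling.
3. If Day 8 is kept for scheduling, require the actual time since last dose to be recorded for PD marrow and blood, and label samples outside the window as a separate post-dosing time point. A Day 8 sample taken 4 to 8 hours after a delayed dose stays in the window.
4. In Section 9.9.2, either exclude post-dosing samples from the last-dose PD summary and the signed rank comparison, or analyse by actual time since dose.

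The cost is wording, one recorded time per sample and slightly fewer samples in the exploratory last-dose summary. Restricting the fallback to dosing days also removes some scheduling room for sites, which step 3 avoids.

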6.2.8 Clinical Laboratory Tests

The following laboratory assessments will be performed at the Screening visit and during the study at the time points as described in Table 4 – Table 7, Appendix K, and Appendices M-O. All samples on dosing days should be drawn predose (≤ 5 hours prior) unless otherwise specified. Laboratory assessments will be recorded in the source document and eCRF and are the following:

- Hematology: CBC including hemoglobin, hematocrit, red blood cell count with indices, WBC count with absolute differential (including blast count) and platelet count.
- Serum chemistry: albumin, total protein, bicarbonate or carbon dioxide (CO₂), corrected calcium (corrected for albumin), C-reactive protein (CRP), ferritin, magnesium, phosphorus, creatinine, urea/blood urea nitrogen (BUN), glucose (fasting ≥ 4 hours), potassium, sodium,

chloride, total bilirubin (fractionate if outside normal range), alkaline phosphatase, AST (SGOT), ALT (SGPT), LDH, and uric acid.

- Additional monitoring for TLS (bicarbonate or CO2, phosphorous, creatinine, urea/BUN, potassium, sodium, chloride, LDH, and uric acid) performed in Cycle 1 on Days 1, 2, and 3 at 12 hours (± 1 hour) postdose.
- Additional serum Ca (corrected for albumin) and Mg tests performed in Cycle 1 on dosing days at 6 and 12 hours (± 1 hour) postdose and in Cycles ≥ 2 prior to dosing. For subjects experiencing Grade ≥ 2 hypocalcemia in Cycle 1, additional serum Ca (corrected for albumin) and Mg tests will be performed all dosing days at 6 and 12 hours (± 1 hour) postdose in Cycles ≥ 2. Additional serum PTH tests performed in Cycle 1 on dosing days at 6 hours (± 1 hour) postdose.

NOTE: In the event of Grade ≥ 2 hypocalcemia and abnormal levels of serum albumin, a serum ionized calcium test and more frequent calcium monitoring must be performed (refer to Section 7.2.13.2). Hypocalcemia adverse event grading should be reported as the highest grade determined.

- G6PD at Screening only
- Special calcium metabolism monitoring tests:
 - serum PTH, total P1NP, and serum β -CTx
 - urine calcium/creatinine ratio obtained from spot (random) urine collection
- Serum 25-hydroxyvitamin D level
- Special chemistry: amylase, lipase, T-cell subsets (cluster of differentiation [CD]4+ and CD8+), thyroid-stimulating hormone (TSH; if abnormal reflex to free thyroxine)

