- ^j In the event of Grade ≥ 2 hypocalcemia or symptoms of hypocalcemia (eg, carpopedal spasm, tetany, seizures, etc), subjects must be hospitalized. Also, if Grade ≥ 2 hypocalcemia and abnormal levels of serum albumin occurs, a serum ionized calcium test must be performed. Refer to Section 7.2.13.2 for hypocalcemia management guidelines. Refer to Section 6.2.8 for required days and timing of tests. Subjects who experienced Grade ≥ 2 hypocalcemia during Cycle 1, require testing Days 1-7 at 6 and 12 hours postdose. All other subjects require testing prior to dosing.
- ^k If intra-subject dose escalation occurs, blood samples for PD assays will be collected during the first cycle only at the increased dose; see laboratory manual for details. Multiple blood samples will be collected for this assay on the specified Days 1, 2, 5. Refer to Section 6.6.
- ¹ Bone marrow samples for biomarker PD assessment are mandatory. When applicable (refer to time points in the table above), bone marrow samples for biomarker PD assessment will be obtained at the same time as a scheduled efficacy assessment. If sufficient bone marrow aspirate specimen is not available, peripheral blood may be submitted in place of the BMA specimen for biomarker studies (eg, MRD); see laboratory manual for details. A bone marrow biopsy can be collected in conjunction with an aspirate if it is standard institutional practice. A bone marrow biopsy must be collected if adequate aspirate sample is not attainable; see for details on sending samples to the central laboratory for disease assessment.

- ^m If end of Cycle 2 (Day 28 ± 3 days) samples are obtained on Day 1 of Cycle 3, they must be obtained prior to CC-90009 administration. Additionally, bone marrow aspirates and biopsies may be obtained after a CR is confirmed, if relapse is suspected, or following treatment discontinuation to elucidate effects of long-term treatment or resistance mechanisms. Additional aspirates and biopsies will be collected as clinically indicated based on the Investigator's medical assessment.

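### Post-dose calcium checks in later cycles: Sections 1.2.4 and 7.2.13.2 trigger them after Grade ≥2 hypocalcemia in any cycle, but Section 6.2.8 and the Cycle ≥2 tables only after a Cycle 1 episode

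*Combined protocol and SAP*

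**What the plan says.** Two sections set a broad trigger.

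- **Section 1.2.4:** a subject with Grade ≥2 hypocalcemia in any cycle should be an inpatient for dosing in later cycles and be monitored as in Cycle 1. It gives no hours.
- **Section 7.2.13.2:** the trigger is again any cycle. These subjects should have extra calcium tests at 6 and 12 hours (±1 hour) after dosing, on dosing days of Cycles ≥2.

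Both allow an exception to inpatient dosing for Grade 2 hypocalcemia that lasts under 24 hours and recovers without IV calcium, after discussion with the medical monitor.

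Two operative texts set a narrow trigger.

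- **Section 6.2.8:** calcium and magnesium are tested at 6 and 12 hours "postdose and in Cycles ≥ 2 prior to dosing", the first part applying to Cycle 1. The later-cycle post-dose tests are added by a sentence that begins "For subjects experiencing Grade ≥ 2 hypocalcemia in Cycle 1, additional serum Ca (corrected for albumin) and Mg tests".
- **Table 36, footnote j:** "Subjects who experienced Grade ≥ 2 hypocalcemia during Cycle 1, require testing Days 1-7 at 6 and 12 hours postdose", followed by "All other subjects require testing prior to dosing". For scheduling it says "Refer to Section 6.2.8 for required days and timing of tests".

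Footnote j of Tables 5, 7, 32, 34 and 38 also names only Cycle 1.

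**The concern.** A subject whose first Grade ≥2 episode falls in Cycle 2 or later is covered by 1.2.4 and 7.2.13.2 but not by 6.2.8 or footnote j. The visit table and the laboratory section are what a site uses to schedule blood draws, and both give the narrower rule.

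The episode itself is managed under Table 11. What may be missed is a recurrence in a later cycle. These subjects have already had Grade ≥2 hypocalcemia on the drug. With predose samples alone, a fall after dosing might not be seen until the next day's sample, and the Table 11 measures begin only once it is found. Daily predose calcium, supplementation, usual inpatient dosing and 6 h vital signs (Table 36, footnote f) reduce the risk, but none of them supplies a post-dose calcium value.

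Section 1.2.3.1 reports hypocalcemia of any grade in 64 of 82 subjects (78.0%). That shows the event is common, but not how often a first Grade ≥2 episode occurs after Cycle 1.

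**Working it through.** **The texts applied to one case.** Take a Part B Days 1-7 subject with a first Grade ≥2 episode in Cycle 2, no exception granted, who starts Cycle 3.

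| Source | Trigger | Calcium tests in Cycle 3 |
|---|---|---|
| 1.2.4 | any cycle | as in Cycle 1 |
| 7.2.13.2 | any cycle | 6 h and 12 h post-dose added |
| 6.2.8 | Cycle 1 | predose |
| Table 36, footnote j | Cycle 1 | predose |
| Table 36, footnote e | any cycle | no test named; inpatient dosing |

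Within Table 36, then, footnote e brings this subject in for inpatient dosing because of the hypocalcemia, while footnote j does not add the post-dose calcium that 7.2.13.2 pairs with that admission.

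**Inputs.** The predose window comes from 6.2.8: "All samples on dosing days should be drawn predose (≤ 5 hours prior) unless otherwise specified". Post-dose draws are at 6 ± 1 h and 12 ± 1 h (6.2.8 and 7.2.13.2). There are seven dosing days, and doses are assumed to be 24 h apart.

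**Samples per Days 1-7 cycle**
- Narrow trigger: 7 predose samples.
- Broad trigger: 7 + (2 × 7) = 7 + 14 = 21 samples.

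**Longest gap between samples on dosing days, nominal times**
- Predose only (0 and 24 h): 24 h.
- With post-dose draws (0, 6, 12 and 24 h): max(6, 6, 12) = 12 h.

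**Longest gap at the edges of the windows**
- Predose only: 24 − (−5) = 29 h.
- With post-dose draws: max(7 − (−5), 13 − 5, 24 − 11) = max(12, 8, 13) = 13 h.

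**First calcium value after a dose**
- Predose only: 24 − 5 = 19 h, up to 24 h. This applies to doses followed by another dosing day. After the Day 7 dose the next scheduled calcium is the Day 8 chemistry panel, a non-dosing visit with a ±2 day window.
- With post-dose draws: 6 ± 1 h, that is 5 to 7 h, after every dose.

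**Draws at stake per subject.** A first episode in Cycle 2 gives 2 × 14 = 28 post-dose draws over Cycles 3 and 4. Sections 3.1 and 6.4 allow treatment beyond Cycle 4, at 14 more per cycle, so a fifth cycle gives 42.

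**Who is exposed.** Table 36 governs the two new Part B cohorts, each of up to 40 evaluable subjects (Figure 4 footnote). The other five tables serve cohorts closed to enrollment (Sections 1.2.3.1 and 3.1).

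**The case against.** The strongest reply is that the texts can be read together. Footnote j says other subjects are tested before dosing; it does not say only before dosing. Section 7.2.13.2 describes additional monitoring, so a site that does those draws complies with every section. A site that has just managed an episode will probably have 7.2.13.2 open, because footnote j also says "Refer to Section 7.2.13.2 for hypocalcemia management guidelines", and the any-cycle rule stands directly above Table 11. The NOTE in 6.2.8 points to 7.2.13.2 as well, stating that "a serum ionized calcium test and more frequent calcium monitoring must be performed" when albumin is also abnormal.

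This makes omission less likely, and that much stands. It does not remove the conflict: on days and timing, footnote j defers to 6.2.8, which has the narrow trigger, and the NOTE concerns a current episode rather than scheduled tests in a later cycle.

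A second reply is that no within-day fall has been shown. In monkeys the drop was first seen on Day 3 of dosing, and it was mild with supplementation (Section 1.2.2). It is fair that the size of the harm is not established. The protocol nevertheless chose post-dose sampling for subjects with a prior episode, and nothing in it explains why the cycle of that episode should matter.

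Smaller points also stand without changing the conclusion. Section 1.2.4 states no hours; those come from 7.2.13.2 and 6.2.8. Cycle 1 monitoring in 6.2.8 also includes post-dose parathyroid hormone and tumor lysis tests, which a change of trigger would not extend to later cycles. No endpoint or analysis is affected.

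**Conclusion.** The concern holds. The operative schedule states a narrower safety rule than Sections 1.2.4 and 7.2.13.2, and footnote e of Table 36 suggests that the any-cycle trigger is the intended one. For an affected subject, the difference is 7 samples against 21 per Days 1-7 cycle, and a longest gap on dosing days of 24 h against 12 h nominally, or 29 h against 13 h with the windows. The gaps assume 24 h dosing intervals. All these figures compare the two schedules; they do not measure risk.

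The number of subjects with a first Grade ≥2 episode after Cycle 1 and a further cycle cannot be derived from the protocol. Any effect on the Part B toxicity rule is at most marginal, since Table 15 counts subjects, and the conclusion does not rely on it. The correction should be made, because the affected subjects have already shown the toxicity and the change is small.

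**What to change.** Change only the trigger words.

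- **Section 6.2.8:** in the sentence that adds post-dose tests in Cycles ≥2, replace the reference to Cycle 1 with *in any prior cycle*.
- **Table 36, footnote j:** replace the reference to Cycle 1 with *during any prior cycle*.
- **Tables 5, 7, 32, 34 and 38, footnote j:** make the same edit for conformity. Table 38 serves the Days 1-10 schedule but its footnote names Days 1-7; that can be corrected in the same pass.

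Leave the brief Grade 2 exception in 1.2.4 and 7.2.13.2, and do not copy it into 6.2.8 or footnote j. Neither now exempts a subject after a Cycle 1 episode, so adding it would remove tests that are currently required. The conflict should not be settled by narrowing 1.2.4 and 7.2.13.2 to Cycle 1, which would withdraw a stated safeguard.

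The cost is the wording plus up to 14 post-dose calcium and magnesium draws per remaining Days 1-7 cycle for each affected subject. Section 7.2.13.2 already calls for the calcium, and 6.2.8 adds the magnesium. These subjects are normally inpatients. One given the exception and dosed in a Limited Stay Unit would have to be available for the 12 h draw, as 6.2.8 already requires after a brief Grade 2 episode in Cycle 1.
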